6.3.3 Dressing shrinkage evaluation

Dressing shrinkage, if any, will be evaluated by measuring surface areas of the dressings at the time of their application and during their removal.

6.4 Wound assessment visits – Weekly visits (Every 7 days \pm 2 days) and final visit

Subjects must undergo dressing changes and wound assessments once every week. Analgesic(s) use will be recorded, and subjects will be asked to report any change in medication during their visits. Assessments carried out will be identical to those described in sections 6.2.2, 6.2.3, and 6.2.4, and sections 6.3.1, 6.3.2, and 6.3.3. The final visit will be the visit eight weeks from the subject's initial visit or whenever the wound is healed (whichever happens first). Dressings will be removed, and all the assessments will be carried out. Information will be recorded on the CRFs.

7 ADVERSE EVENTS

7.1 Definition of Adverse Event

In this study, an adverse event (AE) is any untoward medical occurrence related to the wound or treatment of the wound, including infection or a significant increase in pain during dressing changes.

7.2 Definition of Serious Adverse Event

The FDA definition of a serious adverse event (SAE) will be used in this study: An AE or suspected adverse reaction is considered "serious" if, in the view of either the investigator or sponsor, it results in any of the following outcomes:

- Death
- A life-threatening adverse event
- Inpatient hospitalization or prolongation of existing hospitalization
- A persistent or significant incapacity or substantial disruption of the ability to conduct normal life functions or,
- A congenital anomaly/birth defect.

Important medical events that may not result in death, be life-threatening, or require hospitalization may be considered serious when, based upon appropriate medical judgment, they may jeopardize the participant and may require medical or surgical intervention to prevent one of the outcomes listed in this definition. All SAEs will be reported to Medline, regardless of potential relationship to the wound or treatment of the wound. SAEs will be reported to the reviewing IRB as necessary according to their rules.

7.3 Severity of Adverse Event

The severity of all AEs will be graded on a scale of one through five according to the Common Terminology Criteria for AE guideline, where each grade represents a unique clinical description based on this general guideline:

- **Grade 1:** Mild; asymptomatic or mild symptoms; clinical or diagnostic observation only; intervention not indicated.

- **Grade 2:** Moderate; minimal, local or noninvasive intervention indicated; limited age-appropriate instrumental activities of daily living.
- **Grade 3:** Severe or medically significant but not immediately life-threatening; hospitalization or prolongation of hospitalization indicated; disabling; limiting activities of daily living involving self-care.
- **Grade 4:** Life threatening consequences; urgent intervention indicated
- **Grade 5:** Death related to AE

7.4 Relatedness of Adverse Event and Serious Adverse Event

- **Unrelated:** This category applies to those adverse events which, after careful consideration, are clearly and incontrovertibly due to extraneous causes (disease, environment, etc.)
- **Possible:** This category applies to those adverse events for which, after careful medical consideration at the time they are evaluated, a connection with the Investigational Product administration appears unlikely but cannot be ruled out with certainty.
- **Probable:** This category applies to those adverse events which, after careful medical consideration at the time they are evaluated, are felt with a high degree of certainty to be related to the Investigational Product.
- **Definite:** This category applies to those adverse events which, after careful consideration, are clearly and incontrovertibly due to the Investigational Product.

7.5 Expectedness

The site PI will be responsible for determining whether an AE or SAE is expected or unexpected. An AE will be considered unexpected if the nature, severity, or frequency of the event is not consistent with the risk information previously described for the study intervention.

Expected AEs include a reaction or irritation at the wound site following application of the wound device or infection.

7.6 Adverse Event Reporting

The AEs will be recorded on the AE form by the study staff and reviewed by the site PI. Changes in the severity of an AE will be documented to allow an assessment of the duration of the event at each level of severity. Changes in severity will necessitate a new CRF to document the new level of severity. AEs characterized as intermittent require documentation of onset and duration of each episode.

Non-serious AEs are to be reported to the study sponsor on a monthly basis for review or as agreed upon with the study sponsor and reported to the IRB per IRB reporting requirements.

7.7 Serious Adverse Event Reporting

The site PI shall complete a SAE Form and submit to the study sponsor as soon as possible, but in no event later than 48 hours after the investigator first learns of the effect. The site PI shall report the SAE to the reviewing IRB, if applicable, according to their reporting requirements. The study sponsor is responsible for conducting an evaluation of the SAE and shall report the results of such evaluation to the FDA and to all reviewing IRBs if applicable within 10 working days after the sponsor first receives notice of the effect. Thereafter, the sponsor shall submit such additional reports concerning the effect as FDA requests.

For questions regarding this process or the event, you may contact your Medline clinical designee or the Medline Director of Clinical Operations:

Name: [name]
[contact]
E-mail: [contact]

8 STATISTICAL CONSIDERATIONS

8.1 Sample Size Determination

A previous pilot study was conducted using a within-subjects design, applying both of the dressings described herein to two different wounds on the same subject, measuring wound reduction and other variables. In that study, the MPS dressing that was used led to a 40% reduction in wound size, whereas the CMS dressing led to a 33% reduction.¹¹ The data was used to determine the appropriate sample size for this study.

A power analysis using G*Power 3.1 for an independent samples t-test indicated that with the above reduction in wound sizes and a 10% standard deviation for each treatment, 68 subjects would be necessary to attain 80% power at a two-tailed alpha of 0.05, assuming a 1:1 assignment to the two dressing groups. A target of 80 subjects will be used in order to account for subjects' lost-to-follow-up and other scenarios that result in incomplete data.

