- Subjects who are pregnant, nursing, or planning to become pregnant during the course of the study.
- Subjects who have known allergies to any ingredient(s) in the clinical products used in this study including silver.
- Subjects who do not wish to use product(s) derived from shellfish.
- Subjects with substance use disorder within the past six months.
- Subjects with active infection and/or currently receiving antibiotic treatment for the wound included in the study.
- Subjects who are currently enrolled in another research study which includes investigational treatment and/or medication.
- Subjects judged by the site PI or sub-investigator to be inappropriate as a subject of this study.
- Subject has previous or current systemic disease(s) which, in the judgement of the site PI, is likely to interfere with the study. However, subjects with well-controlled diabetes mellitus (DM) (HbA1c < 8.5) shall be permitted.
- Subjects who receive any additional product or procedure/activity that could influence wound healing, such as chemical debridement, use of other wound cleansers, additional hydrogel or alginate wound products etc.

Phase: Phase IV, Post-Market

Description of Sites/Facilities Multiple wound care centers

Enrolling Participants:

Description of Study Intervention: Subjects who meet all of the inclusion criteria and none of the exclusion criteria will be randomized to receive either MPS-Ag dressing or CMC-Ag dressing. The wound will be cleansed with Skintegrity® wound cleanser, followed by application of MPS-Ag dressing or CMC-Ag dressing. Compression bandage (CoFlex® TLC Two Layer Compression Bandage system) will be applied over the dressing. The dressings will be changed at least once weekly but can be changed earlier by the clinician depending on the level of exudate. Wound assessments will be carried out weekly. The performance of both the dressings will be evaluated according to the study objectives.

Study Duration: Six-to-Sixty months

Participant Duration: Subject participation is intended to last for eight weeks after application of the dressings. Participant duration will begin upon obtaining informed consent and will end after eight weeks or earlier if the subject's wounds heal completely prior to eight weeks.

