2.3.2. Potential Study Benefits

Through the use of these dressings, subjects may experience faster reduction in wound size, improved skin quality of the periwound tissue, and reduced pain during dressing changes.

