5. STUDY POPULATION

5.1. Inclusion Criteria

A subject will be eligible to participate in the study if he or she satisfies *ALL* of the inclusion criteria below:

- Male or female, ≥ 18 years.
- Subject is able and willing to comply with requirements of this trial protocol.
- Subjects must be able to communicate effectively with study personnel.
- Subject has lower extremity venous ulcer wound, as determined by the site PI.

- Subject has adequate lower extremity arterial circulation as determined by the site PI at the time of enrollment
- Size of subject's wound is between 1cm² and 100cm².
- Duration of subject's wound is < 52 weeks.

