8.4 Data Analysis

Descriptive statistics will be provided for the key endpoints, including measures of central tendency (mean or median, as appropriate), measures of variation (standard deviations, coefficients of variation) and 95% confidence intervals and interquartile ranges, as appropriate. Specifically, these measures will be calculated for:

- Changes in wound size
- Average percent periwound global score reduction
- Subject's pain rating during dressing changes
- Dressing shrinkage determined upon removal of dressings
- Proportion of subjects who develop an infection

The key assessment for differences in dressing performance will be based on the comparison of mean reduction in wound size for each dressing type. The specific details of the statistical testing will be provided in a forthcoming SAP. Comparisons of reduction in PUSAS score, subject pain ratings, and dressing shrinkage will also be made between the two dressing types, with specific details described in the SAP.

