8.5 Interim Analysis

The most current version of PASS software Using PASS 2022 (Power Analysis and Sample Size Software (2022). NCSS, LLC. Kaysville, Utah, USA, ncss.com/software/pass) was used to estimate conditional power at $n=46$. It was determined that at $n=46$, a power of 80.65% could detect a mean difference of 7, with a non-inferiority margin of 0.5, at a target alpha-level of 0.05. The assumed population means are 40 and 33, with known standard deviations of 10 and 10. These results are based on one-sided t-test group sequential testing with 3 stages and boundary values calculated from spending functions. Since it is expected that 80% power has been achieved with $n=46$ cases, it is a reasonable time to perform in interim analysis to test for early efficacy and/or futility.

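### The stated 80% power rests on an unsourced SD of 10 that leaves room for less than one healed wound per arm, although healed wounds enter the comparison of means at 100%

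*Combined protocol and SAP*

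**What the plan says.** Section 8.1 takes its means from a pilot in which "the MPS dressing that was used led to a 40% reduction in wound size, whereas the CMS dressing led to a 33% reduction". It then states that "with the above reduction in wound sizes and a 10% standard deviation for each treatment, 68 subjects would be necessary to attain 80% power", for a two-sided independent-samples t-test at 0.05 with 1:1 allocation. The enrolment target is 80, to cover incomplete data. Section 8.5 reuses the inputs: "The assumed population means are 40 and 33, with known standard deviations of 10 and 10". Section 8.4 states that "The key assessment for differences in dressing performance will be based on the comparison of mean reduction in wound size for each dressing type" and leaves the details of the test to a later SAP. Section 2.1 makes clear that the reduction is a percentage.

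On healing, the synopsis says that participation "will end after eight weeks or earlier if the subject's wounds heal completely prior to eight weeks". Footnote a of the Schedule of Activities and section 4.2 say the same in substance. Section 6.4 makes the visit at which the wound is healed the final visit. Section 8.3 counts as evaluable anyone with valid wound size measurements at the initial and final visits. Section 5.1 admits small ulcers: "Size of subject's wound is between 1cm² and 100cm²".

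**The concern.** Read together, sections 6.4, 8.3 and 8.4 bring each healed subject into the key comparison with a reduction of 100%. That is 60 points above one planning mean and 67 above the other, or six and nearly seven of the planned SDs. A few such values inflate the SD well beyond 10. If the SD is too small, so is the sample size for a t-test, and the 80% on which the trial relies is too high. The plan reports no pilot SD, pilot follow-up time, expected healed share, or power at any other SD, so a reader cannot judge how robust the figure is.

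**Working it through.** **Inputs.** Means 40 and 33, SD 10 per arm, two-sided alpha 0.05, t-test, 34 per arm (68) or 40 per arm (80): all from section 8.1. Healed share: not in the documents, so assumed.

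**1. The plan's own figure.** The standardised difference is (40 − 33)/10 = 0.7. The noncentral t calculation gives 33.02 per arm, rounded up to 34, so N = 68 with power 81.2%. At 40 per arm it is 87.1%. The arithmetic in 8.1 is correct; the question is the SD that goes into it.

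**2. How many healed wounds SD 10 can hold.** The one-sided Chebyshev (Cantelli) bound applies to any distribution with mean m:

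P(reduction ≥ 100) ≤ SD² / (SD² + (100 − m)²)

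- m = 40: 100/(100 + 60²) = 100/3,700 = 2.7%, and 0.027 × 34 = 0.9 subjects
- m = 33: 100/(100 + 67²) = 100/4,589 = 2.2%, and 0.022 × 34 = 0.7 subjects

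Even these ceilings are reached only if every unhealed wound in the arm shrinks by the same percentage.

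**3. Power over a range of healed shares.** Assume that a share p heals in each arm, the overall means stay at 40 and 33, and unhealed wounds vary with SD 10. The unhealed mean is then u = (m − 100p)/(1 − p), and the overall variance is (1 − p)·10² + p(1 − p)(100 − u)². For p = 5% and m = 40: u = 35/0.95 = 36.8, variance = 95 + 0.0475 × 63.16² = 284.5, SD = 16.9. Power is from simulated t-tests, because the mixture is far from normal.

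| Healed share | Unhealed means | SD per arm | Pooled SD | Power, 34 per arm | Power, 40 per arm |
|---|---|---|---|---|---|
| 3% | 38.1 / 30.9 | 14.4 / 15.4 | 14.9 | about 51% | about 57% |
| 5% | 36.8 / 29.5 | 16.9 / 18.2 | 17.5 | about 40% | about 45% |
| 10% | 33.3 / 25.6 | 22.1 / 24.3 | 23.2 | about 26% | about 29% |
| 20% | 25.0 / 16.25 | 31.3 / 34.7 | 33.0 | about 14% | about 16% |

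Simulation error is within about one point. The ordinary t-test formula at the same pooled SDs gives slightly lower figures (37% and 23% at 34 per arm for 5% and 10% healed).

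**4. Power over a range of SDs, difference 7.** This uses the formula behind 8.1 with no healing assumption.

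| SD | 34 per arm | 40 per arm |
|---|---|---|
| 10 | 81% | 87% |
| 15 | 47% | 54% |
| 20 | 30% | 34% |
| 30 | 16% | 18% |

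By the table in step 3, SD 15 corresponds to about 3% healed, SD 20 lies between 5% and 10%, and SD 30 lies between 10% and 20%.

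**The case against.** **The exit rules are only contingencies.** They say what happens if a wound heals and imply no expected share. This stands. A reader might infer that the planning figures contradict the follow-up rule, but the documents do not support that: a rule for a possible event is compatible with its being rare. What remains is that 8.1 does not say that it must be rare.

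**The figures come from a pilot.** Section 8.1 does say that pilot data informed the sample size. It reports only the two means, however, from a within-subject comparison, and does not say where the SD of 10 came from or whether any pilot wound healed.

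**The loss depends on the test, which the SAP has yet to fix.** This largely stands. In the mixture of step 3 at 40 per arm, a rank test keeps about 81%, 76% and 64% power at 5%, 10% and 20% healed. Much of the loss is therefore specific to the t-test, and it would go too far to call a null result uninformative whatever the analysis. But 8.1 computes its power for a t-test and 8.4 bases the key assessment on means, so the stated figure has to be judged on those terms.

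**The step 3 powers are not ceilings.** One might put the smallest SD compatible with a healed share into the t-test formula and read the result as the most power attainable. For 5%, 10% and 20% healed at 34 per arm that gives 50%, 27% and 15%. Simulating that same case, with all unhealed wounds identical, gives 56%, 33% and 16%, so those values are not upper bounds.

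**The endpoint ignores speed.** Section 2.3.2 says that "subjects may experience faster reduction in wound size", and a reader might conclude that the primary endpoint should be replaced by a time-averaged area. That sentence describes a possible benefit to subjects. The primary objective is change in wound size. A replacement would change what is estimated, and no gain in power has been shown for it.

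**Conclusion.** The point holds as a fault in a planning input, not in the calculation. The result that needs no assumption about healing is the ceiling: SD 10 allows at most 2.7% and 2.2% of subjects at 100%, less than one per arm of 34. The t-test power in 8.1 is therefore credible only if almost no wound heals in eight weeks, a condition that the plan neither states nor supports.

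The size of the loss is conditional. It rests on an assumed healed share that is equal in both arms, a difference held at 7, SD 10 among unhealed wounds, and a t-test. Under those assumptions about 3% healed, roughly one subject per arm, already brings power to about one half at either planned size. If healing differed between arms, the difference in means could change too, and the 40 and 33 would need restating as well. Enrolling 80 rather than 68 adds only a few points.

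**What to change.** In section 8.1:

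- State where the SD of 10 comes from, over what follow-up it was observed, and whether healed wounds were included.
- Restate the t-test power at the planned size for SDs from 10 to 30, as in step 4, with the assumed share healed by week 8 beside each SD.

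In section 8.5, use the same SDs and healed shares, since it now repeats the means and SDs of 8.1.

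The cost is a change of wording and a short recalculation. It needs no new data or visits, and no change to the primary endpoint or to enrolment is proposed here. The downside is that the stated power becomes less favourable at every SD above 10.

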1. PROTOCOL SUMMARY

1.1. Synopsis

Title: A comparative evaluation of a marine polysaccharide dressing and a carboxymethylcellulose dressing on subjects with lower extremity venous ulcers.

Study Description: Venous leg ulcers are lower extremity ulcers that develop due to sustained venous hypertension resulting from chronic venous insufficiency. Varicose veins, deep vein thrombosis, poor calf muscle function, arterio-venous fistulae, obesity, and history of leg fracture are some of the risk factors for venous ulceration. Numerous dressing types exist to treat these ulcers. This study will compare a marine polysaccharide (MPS) dressing (Opticell® Ag⁺ dressing manufactured by Medline Industries, LP, referred to as MPS-Ag) to a carboxymethylcellulose (CMC) dressing (Aquacel® Ag Advantage dressing manufactured by ConvaTec, referred to as CMC-Ag), and will determine which dressing better manages these wounds with regard to wound size and periwound skin condition. Subjects will be randomized to receive either MPS-Ag dressing or CMC-Ag dressing.

Objectives: **Primary objective:** Evaluate and compare wound size changes in subjects when either MPS-Ag dressing or CMC-Ag dressing is used.

Secondary objectives: Compare (1) periwound skin condition, (2) subject perception of pain during dressing changes, and (3) dressing shrinkage.

Endpoints: **Primary endpoint:** Changes in wound size in subjects when MPS-Ag dressing or CMC-Ag dressing is used.

Secondary endpoints: (1) Evaluation of peri-ulcer skin assessment scale (PUSAS) score weekly for entire duration of study, (2) Subjective evaluation of subject pain perception during dressing changes using a numerical pain scale, and (3) Change in surface area of the dressing.

Study Population: Sixty-eight adult subjects with lower extremity venous ulcers will be selected.

Inclusion criteria will be:

- Males and females, 18 years or older.

- Subject is able and willing to comply with requirements of this trial protocol
- Subjects must be able to communicate effectively with study personnel
- Subject has lower extremity venous ulcer wound, as determined by the site Principal Investigator (PI).
- Subject has adequate lower extremity arterial circulation as determined by the site PI at the time of enrollment.
- Size of subject's wound is between 1cm² and 100cm².
- Duration of subject's wound is <52 weeks.

Exclusion criteria will be:

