4.2. End of Study Definition

A subject's participation in the study may end at several critical points:

- Subject's wound heals, as determined by the site PI.
- Subject develops an infection at the wound site or any significant medical condition in the opinion of the site PI that precludes his/her continuation in the study.
- Subject has completed eight weeks of treatment.
- Subject withdraws from the study for any reason.

If the subject withdraws from the study, he or she will be replaced by another subject.

A clinical study report that has been approved by the Clinical Affairs Director will be issued following completion of the study.

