6.3.2 Infection evaluation

During dressing change visits, the wound site included in the study will be evaluated for development of any infection. In the event of a suspected infection, clinical staff will collect a wound culture. Should a subject develop an infection as confirmed by wound culture, this will be noted as an adverse event (AE) and his or her participation in the study will be terminated. Subject participation will also be terminated if they receive any antibiotic, prophylactic or therapeutic, for treatment of the wound site included in the study.

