8.3 Populations for Analyses

An evaluable population will be used for all analyses, with evaluable defined as any subject with valid initial visit and final visit wound size measurements.

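### The synopsis gives 68 as the number of subjects to be selected, but Section 8.1 needs 68 in the analysis and targets 80, and the replacement rule in Section 4.2 does not settle the total

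*Combined protocol and SAP*

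**What the plan says.** - **Section 1.1 (Synopsis, Study Population):** "Sixty-eight adult subjects with lower extremity venous ulcers will be selected". Nothing there says that these are evaluable subjects or completers.
- **Section 8.1:** with pilot reductions of 40% and 33% and "a 10% standard deviation for each treatment, 68 subjects would be necessary to attain 80% power", using a two-sided 5% independent-samples t-test and 1:1 allocation. It then adds: "A target of 80 subjects will be used in order to account for" loss to follow-up and "other scenarios that result in incomplete data". No loss rate is given.
- **Section 8.3:** all analyses use the evaluable population, defined as "any subject with valid initial visit and final visit wound size measurements".
- **Section 4.2:** lists four ways in which participation may end: healing, infection or a significant medical condition, completion of eight weeks, and withdrawal for whatever reason. It then says: "If the subject withdraws from the study, he or she will be replaced by another subject". No maximum or total is attached.
- **Section 6.3.2:** if infection is confirmed by culture, "his or her participation in the study will be terminated". Participation also ends if the subject receives any antibiotic for the study wound.

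**The concern.** The synopsis uses as an enrolment figure the number that Section 8.1 requires after losses. Someone working from the synopsis could stop recruitment at 68 with no margin, although the sponsor's own calculation allows for losses by going to 80.

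The replacement rule might have reconciled the two numbers, but it is tied to neither. It speaks of a subject who withdraws, which Section 4.2 lists separately from infection. It is silent on three matters:

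- whether a subject terminated for infection or antibiotics is replaced;
- whether a subject without a valid final measurement is replaced;
- whether replacements use up the 80 or are added to it.

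Four totals are therefore open: 68, 68 plus replacements, 80, or 80 plus replacements. Section 8.2 has each site randomise from its own list without central coordination, so the total needs to be unambiguous.

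**Working it through.** **Inputs from Section 8.1.** Difference 40 − 33 = 7 points; SD 10 in each arm; two-sided alpha 0.05; 1:1 allocation; independent-samples t-test; target 80.

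**Step 1: reproduce the 68.** Power comes from the noncentral t distribution with N − 2 degrees of freedom and noncentrality 7 / (10 × √(2/n)), where n = N/2 per arm.

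- n = 33 (N = 66): power 79.97%, just short of 80%.
- n = 34 (N = 68): noncentrality 7 / (10 × √(2/34)) = 2.886, 66 degrees of freedom, power 81.2%.

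So 68 is reproduced as the number needed in the analysis.

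**Step 2: reproduce the 80.** 1 − 68/80 = 0.15, and 68 / (1 − 0.15) = 80. The target of 80 is what 68 evaluable subjects require at 15% loss. The protocol does not state this rate; it is implied by the two numbers.

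**Step 3: compare the two enrolment numbers.** Loss rates are assumptions, and analysed numbers are rounded to whole subjects.

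| Enrolled | Loss | Replacement | Analysed | Power |
|---|---|---|---|---|
| 68 | 10% | none | 68 × 0.90 ≈ 61 | about 77% |
| 68 | 15% | none | 68 × 0.85 ≈ 58 | about 74.5% |
| 68 | 20% | none | 68 × 0.80 ≈ 54 | about 71% |
| 68 | 15% | half of losses | 68 × 0.925 ≈ 63 | about 78% |
| 68 | 15% | all losses | 68 | 81% |
| 80 | 10% | none | 80 × 0.90 = 72 | 83% |
| 80 | 15% | none | 80 × 0.85 = 68 | 81% |
| 80 | 20% | none | 80 × 0.80 = 64 | 79% |

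**Step 4: what the counting rule changes.** At 15% loss from 80, 0.15 × 80 = 12 subjects are lost. If all 12 were replaced on top of the 80 and every replacement completed, 80 + 12 = 92 would be randomised and 80 analysed, with power 87%. If replacements count within the 80, no more than 80 are randomised. The text allows either reading.

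**Limit of these figures.** They are for the fixed-sample two-sided test of Section 8.1. Section 8.5 plans an interim analysis at n = 46 with spending-function boundaries. If that spending also governs this test, the final alpha would be below 0.05 and power somewhat lower. As an illustration only, a final alpha of 0.045 gives 79.9% at 68 analysed. Section 8.4 leaves the details of testing to the SAP.

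**The case against.** The strongest reply is that Section 8.1 is the operative sample-size section. It sets 80 and says why, and the number is coherent with 68 evaluable at 15% loss. On that view the synopsis is only a summary that was not updated, or that means evaluable subjects. This stands as a limit on the consequence: power suffers only if recruitment follows the synopsis. It does not remove the conflict. The synopsis speaks of subjects selected, and no section says that its 68 means completers.

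A second reply is that Section 4.2 replaces withdrawals, so the no-replacement rows are a worst case. That also stands. Withdrawal for whatever reason could be read to include loss to follow-up, and full replacement would make 68 sufficient. But infection is a separate item in the same list, and neither antibiotic termination nor a missing valid final measurement is mentioned in the rule. If 68 meant completers reached by replacement, the allowance to 80 would be largely redundant.

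A third reply is that termination for infection need not make a subject non-evaluable, since wound size is recorded weekly and Section 8.3 asks only for valid initial and final measurements. The protocol does not say whether the last measurement before termination counts as the final one. This leaves the number of losses uncertain; it does not settle the total.

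A reader might also infer that power collapses once a second subject is lost from 68. It does not: 66 analysed gives 79.97%, and the decline from there is gradual. The losses that matter are in the 10% to 20% range.

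**Conclusion.** The point holds as an inconsistency in the current text. The synopsis states as enrolment the number that Section 8.1 needs in the analysis, and Section 4.2 does not reconcile 68 with 80. The size is moderate. If 68 were enrolled, power would be about 77% to 71% at an assumed 10% to 20% unreplaced loss, and about 78% if half of a 15% loss were replaced. Under the sponsor's own target of 80 with the implied 15% loss it would be 81%. All of this rests on the difference and SD of Section 8.1, on assumed loss rates, and on no alpha being spent at the interim.

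Two stronger readings are not supported. A reader might infer that the trial is underpowered or that 68 was miscalculated. The calculation reproduces, and Section 8.1 already carries an allowance for losses. A reader might also infer that the SD of 10 is too small, because Section 8.1 shows no pilot SD. The documents contain nothing that shows it to be wrong, and the enrolment conflict does not depend on it.

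**What to change.** 1. **Synopsis, Study Population:** replace the sentence with *Eighty subjects will be randomised to obtain 68 evaluable subjects.*
2. **Sections 1.1, 4.2 and 8.1:** reconcile them by stating which losses are replaced (withdrawal, loss to follow-up, termination for infection or antibiotics, no valid final measurement) and whether replacements count within the 80 or are added to it.

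The cost is one sentence in the synopsis and a short clarification in Section 4.2, cross-referred to Section 8.1. The change adopts the sponsor's own target. It asks for no enrolment beyond the planned 80 and alters no rule on when a subject's participation ends.
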